## **17 USE OF INFORMATION AND PUBLICATION**

CTI BioPharma Corp. recognizes the importance of communicating medical study data and therefore encourages their publication in reputable scientific journals and at seminars or conferences. The Clinical Study Agreement will describe the details of the processes of producing and reviewing reports, manuscripts, and presentations based on the data from this study.

## **19 APPENDICES**

### Appendix 1 - Selected Strong Inhibitors of CYP3A4

boceprevir	nefazodone
ciprofloxacin	nefinavir
clarithromycin	norfloxacin
conivaptan	posaconazole
erythromycin	quinidine
fluconazole	ritonavir
grapefruit	saquinavir
grapefruit juice	Seville oranges
indinavir	star fruit
itraconazole	telaprevir
ketoconazole	telithromycin
lopinavir	troleandomycin
mibefradil	voriconazole

This list is not comprehensive. When considering using an agent that could be a potential CYP3A4 inhibitor, please discuss this with the medical monitor.

Source: <http://medicine.iupui.edu/clinpharm/ddis/table.asp> and <http://www.pharmacytimes.com/issue/pharmacy/2008/2008-09/2008-09-8687>.

## Appendix 2 – Selected Strong Inducers of CYP450

carbamazepine

efavirenz

nevirapine

phenobarbital

phenytoin

pioglitazone

rifabutin

rifampin

St. John's Wort

troglitazone

This list is not comprehensive. When considering using an agent that could be a potential CYP450 inducer, please discuss this with the medical monitor.

Source: <http://medicine.iupui.edu/clinpharm/ddis/table.asp> and <http://www.pharmacytimescom/issue/pharmacy/2008/2008-09/2008-09-8687>.

### Appendix 3 - Common Terminology Criteria for Adverse Events: Diarrhea (Version 4.03)

Definition: A Disorder Characterized by Frequent and Watery Bowel Movements.	
1	Increase of < 4 stools per day over Baseline; mild increase in ostomy output compared to Baseline
2	Increase of 4 – 6 stools per day over Baseline; moderate increase in ostomy output compared to Baseline
3	Increase of $\geq 7$ stools per day over Baseline; incontinence; hospitalization indicated; severe increase in ostomy output compared to Baseline; limiting self-care ADL
4	Life-threatening consequences; urgent intervention indicated
5	Death

## **Appendix 4 - Investigator Responsibilities, Required Documentation, and Signature**

CTI BioPharma Corp. will select the investigator(s) on the basis of their expertise in the field of clinical studies in hematologic oncology and in the care and treatment of patients with chronic myeloproliferative diseases. Investigators will also be selected on the appropriateness of their facility to conduct a research study of this nature, and the characteristics of the patient population treated at the institution. The investigator will:

- Obtain Institutional Review Board (IRB), Research Ethics Board (REB), or Independent Ethics Committee (IEC) approval of the protocol and amendments to the protocol and Informed Consent Form before initiation of the protocol or any amendments for the study, and obtain annual IRB or IEC renewal, as required.
- Ensure that current FDA and/or ICH-E6 regulations are followed.
- Select all patients in accordance with the selection criteria outlined in the study protocol.
- Treat and follow patients as described in this research protocol. Complete all electronic case report forms (eCRFs) in a timely manner and review eCRFs for accuracy and completeness. Provide the original clinical source documents to verify all data entered on eCRFs or SAE reports and all data that document the course of the patient throughout their participation on the study. Provide a clinical summary to the Sponsor's clinical research monitor.
- Report all adverse events to CTI BioPharma Corp. or designee, as required by the protocol.
- Ensure that the investigational drug is kept in a secured, limited access area and stored under proper conditions. Ensure that all investigational drug receipt and dispensing information is recorded and all drug can be accounted for at all times.
- Before initiation of the study, each participating investigator will submit to CTI:
  - FDA Form 1572 and, if applicable, other ministry of health required forms
  - Copies of the medical licenses of principal investigators and subinvestigators
  - Addresses and descriptions of all clinical laboratory facilities to be used
  - Laboratory certification and expiration dates
  - Normal ranges and effective dates for all required laboratory tests
  - IRB/REB/IEC approval letter referencing the protocol (and amendments, if applicable)
  - IRB/REB/IEC Membership List: A list of the IRB/REB/EC members, their respective titles or occupations, and their institutional affiliations

- A sample copy of the IRB/REB/IEC-approved Informed Consent Form
- Curricula vitae: Curricula vitae for the principal investigator and all subinvestigators
- Financial disclosure for the principal investigator and all subinvestigators
- Protocol signature page, signed by the principal investigator

## Version History

Version and Date	Description
Version 1.0, 13 September 2021	Initial version

**Table 1: List of Abbreviations and Definitions of Terms**

ABBREVIATION	DEFINITION
AE	Adverse Event
ADI	Actual Dose Intensity
AESI	Adverse Event of Special Interest
ATC	Anatomical Therapeutic Chemical
CI	Confidence interval
CK	Creatine kinase
CMH	Cochran-Mantel-Haenszel
COVID-19	Coronavirus disease 2019
CTCAE	Common Terminology Criteria for Adverse Events
ECG	Electrocardiogram
ECMO	Extracorporeal Membrane Oxygenation
eCRF	Electronic Case Report Form
EOT	End of Treatment
FiO2	Fraction of inspired oxygen
IDMC	Independent Data Monitoring Committee
IMV	Invasive Mechanical Ventilation
MedDRA	Medical Dictionary for Regulatory Activities
PaO2	Arterial oxygen partial pressure
PT	Preferred Term
RDI	Relative Dose Intensity
SAE	Serious adverse event
SAP	Statistical Analysis Plan
SoA	Schedule of Assessments
SMQ	Standardised MedDRA Query
SOC	Standard of care
SpO2	Blood oxygen saturation
TEAE	Treatment-emergent adverse event
TESAE	Serious treatment-emergent adverse event
TFLs	Tables, Figures, and Listings
WHO	World Health Organization
WHODD	World Health Organization Drug Dictionary
WHO-DDE	World Health Organization Drug Dictionary Enhanced

## 1 INTRODUCTION

This Statistical Analysis Plan (SAP) describes the statistical analyses and data presentations to be performed for protocol PAC319, “A Phase 2 Randomized, Double-blind, Placebo-controlled, Multicenter Study of Pacritinib Plus Standard of Care Versus Placebo and Standard of Care in Hospitalized Patients With Severe COVID-19 With or Without Cancer” (Amendment 4).

This document provides additional details concerning the statistical analyses that were mentioned in the protocol. If additional analyses are required to supplement the planned analyses described in this SAP, they will be identified as post hoc in the clinical study report.

## 2 STUDY OBJECTIVES

### 2.1 Primary Objective

To compare the efficacy of pacritinib + standard of care (SOC) versus placebo + SOC in hospitalized patients with severe COVID-19 with or without cancer, as the proportion of patients who require invasive mechanical ventilation (IMV) and/or extracorporeal membrane oxygenation (ECMO) or die by Day 28. Severe COVID-19 is defined as confirmed disease in patients who are hospitalized with hypoxia ( $\text{SpO}_2 \leq 93\%$  on room air at sea level), respiratory rate  $>30$ ,  $\text{PaO}_2/\text{FiO}_2 <300$  but do not require IMV.

### 2.2 Secondary Objectives

1. To compare the number of ventilator-free days, defined as the number of days that patients are alive and not intubated, from randomization to Day 28 between pacritinib + SOC versus placebo + SOC
2. To compare the mortality rate between pacritinib + SOC versus placebo + SOC at Day 28
3. To compare the mortality rate between pacritinib + SOC versus placebo + SOC at Day 15
4. To compare the time to improvement by at least 2 points relative to Baseline on the 7-point ordinal scale of clinical status between pacritinib + SOC versus placebo + SOC
5. To compare the clinical status assessed by the 7-point ordinal scale of clinical status at Days 8, 15, 22, and 28 between pacritinib + SOC versus placebo + SOC
6. To compare the rate of use of immunomodulatory agents as treatment for COVID-19 during the 28 days following randomization between pacritinib + SOC versus placebo + SOC
7. To evaluate the toxicity profile of pacritinib therapy in hospitalized patients with severe COVID-19 with or without cancer

### 2.3 Tertiary Objectives

To evaluate the treatment effects of pacritinib + SOC vs. placebo + SOC on the following markers of disease severity:

- Serum concentrations of C-reactive protein (CRP)
- Serum concentrations of ferritin
- Serum concentrations of D-dimer
- Serum concentrations of Interleukin 6 (IL-6)
- Serum troponin-I
- Serum lactate dehydrogenase (LDH)
- Serum brain natriuretic peptide (BNP)
- Procalcitonin
- Triglycerides
- Creatine kinase (CK)

### **3 STUDY OVERVIEW**

#### **3.1 Study Design**

This is a Phase 2 randomized, double-blind, placebo-controlled, multicenter study to evaluate the efficacy and safety of pacritinib in hospitalized patients with severe COVID-19 with or without cancer. Severe COVID-19 is defined as confirmed disease in patients who are hospitalized with hypoxia ( $\text{SpO}_2 \leq 93\%$  on room air), respiratory rate  $>30$ ,  $\text{PaO}_2/\text{FiO}_2 <300$ , or lung infiltrates  $>50\%$  but do not require IMV.

Patients will be randomized 1:1 to receive pacritinib (400 mg QD on Day 1, then 200 mg BID from Day 2 to Day 14) + SOC or placebo + SOC stratified by age (< 60 years versus  $\geq 60$  years) and the 7-point ordinal scale of clinical status scale (baseline 3 or 4 versus 5). The study duration will be 8 weeks.

Assigned treatment will continue for up to Day 14 or until the patient experiences intolerable adverse events (AEs), withdraws consent, or initiates another investigational therapy, or until the study is terminated. Assigned therapy may be given for an additional 7 days (for a total of 21 days) with the approval of the Medical Monitor if, in the opinion of the investigator, the patient's clinical signs and symptoms are improving and the potential benefit outweighs the potential risk. In the event of hospital discharge, patients will complete treatment with the assigned therapy as an outpatient.

The primary endpoint is the effect of treatment on the proportion of patients who require IMV and/or ECMO or die by Day 28.

Ongoing safety monitoring will be conducted by an independent data monitoring committee (IDMC). The IDMC will comprise a multidisciplinary group of at least three voting members in the fields of hematology, infectious disease, and biostatistics. Additional personnel may be

added to the IDMC at the request of the IDMC membership. The membership, roles, and responsibilities of the IDMC will be fully defined by an IDMC charter.

Safety will be monitored with physical examinations, clinical laboratory assessments, and electrocardiogram (ECG) monitoring for inpatients. Patients who are discharged from the hospital while still on study will be monitored weekly. Outpatient monitoring will include telephone contact and may also include review of the patient's electronic medical record. Laboratory and ECG assessments will not be required for monitoring outpatients, including those completing their course of study drug. Specified pacritinib/placebo dosage modifications will be followed to address identified abnormalities. AE data will be collected from the time of randomization through 30 days following the last dose of pacritinib/placebo. Serious adverse events (SAEs) assessed as related (i.e., possibly related per protocol) to pacritinib/placebo or study procedure by the investigator or Sponsor shall be followed until the event resolves, stabilizes or the patient is lost to follow-up. SAEs assessed as unrelated to pacritinib/placebo or study procedures shall be followed for 30 days after the last dose of pacritinib/placebo, or until the event resolves, returns to baseline, stabilizes, or the patient is lost to follow-up, whichever comes first.

### **3.2 Study Centers**

The study will take place at approximately 21 centers in the United States (number of centers and countries may be reassessed as patient enrollment increases).

### **3.3 Randomization and Blinding**

Eligible patients will be centrally randomized in a 1:1 allocation ratio to receive pacritinib (400 mg QD on Day 1, then 200 mg BID from Day 2 to Day 14) + SOC or placebo + SOC according to a stratified permuted block design stratified by age (< 60 years versus  $\geq$  60 years) and the 7-point clinical status scale (baseline 3 or 4 versus 5).

This study is double-blind; the Sponsor, study patients, and Investigators will be blinded to treatment assignments. The IDMC will have access to unblinded data. Individual patient unblinding may occur at the request of the Investigators if necessary for medical reasons and to assess suspected unexpected serious adverse reactions.

### **3.4 Sample Size Determination**

The study sample size will be approximately 200 patients (randomized in a 1:1 ratio). This provides 80% power to detect at least 13% treatment difference in the proportion of patients who progress to IMV and/or ECMO or die by Day 28, assuming that the response rate is 13.5% in the pacritinib + SOC arm and 26.5% in the placebo+SOC arm, with a one-sided Type I error rate of 0.10.

### 3.5 Duration of Study

The approximate study duration for each patient will be 8 weeks. The estimated duration of the entire study is approximately 1 year if the maximum number of patients are enrolled.

### 3.6 Schedule of Assessments (SoA)

The Schedule of Assessments is presented in Protocol Table 1.

## 4 ANALYSIS POPULATIONS

The study analysis populations and planned analysis for each population are as follows.

**Table 2 Analysis Populations**

Population Name	Planned Analyses	Definition
Intent-to-Treat (ITT) Population	Patient disposition, demographics, clinical baseline characteristics, and efficacy	
The Intent-to-treat (ITT) population is defined as all patients randomized.
 
Note: Patients in this population will be analyzed according to the treatment arm to which they were assigned at randomization. This population will be used for efficacy analyses.

Safety Population	Safety	
The Safety population is defined as all randomized patients who received at least one dose of study treatment.
 
Note: Patients in this population will be analyzed according to the treatment actually received. This population will be used for the analysis of safety endpoints.

## 5 STUDY ASSESSMENTS

### 5.1 Efficacy Assessments

This section describes the assessments that will be performed to evaluate the efficacy endpoints.

#### 5.1.1 Ordinal Scale of Clinical Status

The following scale adapted from [Cao et al.](#) will be used in order to assess the clinical status for the derivation of primary and secondary endpoints.

**Table 3 Ordinal Scale of Clinical Status (adapted from Cao et al.)**

Ordinal Value and Description
1. Not hospitalized with resumption of normal activities
2. Not hospitalized but unable to resume normal activities
3. Hospitalization, not requiring supplemental oxygen
4. Hospitalization, requiring supplemental oxygen not meeting criteria for categories 5 or 6
5. Hospitalization, on non-invasive positive pressure ventilation or high-flow nasal cannula
6. Hospitalization, requiring IMV and/or ECMO
7. Death

### **5.1.2 Marker of Disease Severity Assessments**

The following markers of disease severity will be assessed:

- Creatinine Kinase,
- Serum concentrations of C-reactive protein (CRP),
- Serum concentrations of ferritin,
- Serum concentrations of D-dimer,
- Serum concentrations of IL-6,
- Serum troponin-I,
- Serum lactate dehydrogenase (LDH),
- Serum brain natriuretic peptide (BNP),
- Procalcitonin,
- Triglycerides.

### **5.1.3 Lung Function Assessment**

Lung function will be assessed by SpO2 in ambient air (if possible), SpO2 with oxygen supplementation (if applicable), documentation of oxygen delivery method, highest oxygen delivery flow rate (if receiving noninvasive oxygen), highest fraction of inspired oxygen (%FiO2) (if on continuous positive airway pressure ventilation [CPAP], bilevel positive air pressure (BiPAP), or invasive mechanical ventilation [IMV]), highest positive end-expiratory pressure (PEEP; if on positive pressure ventilation), and lowest PaO2:FiO2 ratio (if arterial blood gas [ABG] is obtained and the patient is on positive pressure ventilation).

### 5.1.4 Immunomodulatory Agents

The use of immunomodulatory agents as treatment for COVID-19 such as corticosteroids, tocilizumab, anakinra, or eculizamab, will be assessed.

## 5.2 Safety Assessments

This section describes the assessments that will be performed to evaluate safety.

Safety assessments include adverse event reporting, laboratory assessments, vital signs, ECG assessments, and physical examinations.

### 5.2.1 Adverse Events

An AE is any untoward medical occurrence in a patient or clinical investigation patient administered a pharmaceutical product and that does not necessarily have to have a causal relationship with this treatment.

AEs will be collected during the clinical study from the time of randomization through 30 days following the last dose of pacritinib/placebo. AEs that occur after the 30-Day Post EOT Visit that are considered possibly related to pacritinib/placebo or procedure should also be recorded. For screened patients who are not randomized, only SAEs occurring between the time of informed consent and determination of screen failure are reported.

The following information should be captured for all AEs: date of onset and resolution, severity per Common Terminology Criteria for Adverse Events (CTCAE), seriousness, the investigator's assessment of relationship to pacritinib/placebo, event outcome, and action taken with study medication due to the reported event. If concomitant treatment is given for the AE, this information should be captured on the appropriate electronic case report form (eCRF). If an AE results in early termination of the patient's pacritinib/placebo treatment period, "AE" should be selected as the reason for discontinuation on the eCRF.

The CTCAE version 4.03 will be used for the grading of adverse events.

**Table 4 Adverse Event Relationship to Pacritinib/Placebo**

Relationship Category	Description
Possible	There is a reasonable causal relationship between the event and pacritinib/placebo, the event occurred within a plausible time relationship to pacritinib/placebo administration, but the event could also possibly be explained by the condition under study, concurrent disease, other drugs or

Relationship Category	Description
	chemicals, or other circumstances. Dechallenge information is lacking or unclear.
Unlikely	There is a temporal relationship of the event to pacritinib/placebo but not a reasonable causal relationship; there is no temporal relationship to pacritinib/placebo administration or the condition under study, concurrent disease, and other drugs or chemicals; or other circumstances provide a plausible explanation for the event.

### 5.2.2 Laboratory Assessments

Clinical laboratory assessments will be performed at the times specified in protocol Table 1. The following clinical laboratory parameters will be evaluated during the study.

**Table 5 Laboratory Assessments and Parameters**

Laboratory Test	Parameters
Serum chemistry	Sodium, potassium, chloride, bicarbonate, blood urea nitrogen, creatinine, glucose, calcium, and magnesium
Liver Panel	AST, ALT, alkaline phosphatase, total bilirubin, and albumin.
Hematology	WBC count, hemoglobin, hematocrit, and platelet count Note: WBC subsets may be reported as either differential or absolute counts on the eCRF. Additional white cell counts (e.g. bands) may also be reported if available.
Coagulation	INR, PTT, and fibrinogen
Other	Ferritin, LDH, CRP, IL-6, Troponin-I, LDH, BNP, procalcitonin, triglycerides, and CK Serum pregnancy test for women of childbearing potential

### **5.2.3 Vital Signs**

Vital signs will be assessed at the times specified in protocol Table 1. The vital signs assessment will include recording of the systolic blood pressure (mmHg), diastolic blood pressure (mmHg), respiratory rate (breaths/minute), maximum temperature, maximum heart rate, SpO2, and body weight.

### **5.2.4 Electrocardiograms (ECGs)**

The ECG assessment will be performed at the times specified in protocol Table 1.

The Fridericia-Corrected QT interval (QTcF) and overall interpretation will be recorded.

### **5.2.5 Physical Examinations**

The Physical Examination assessment will be performed at the times specified in protocol Table 1.

## **6 CLINICAL OUTCOME VARIABLES**

This section describes the clinical outcomes and derivation of variables considered for this study.

### **6.1 Primary Efficacy Endpoint**

The primary endpoint is the proportion of patients with progression to IMV and/or ECMO or death by Day 28 (+/- 2 days) for the Intent-to-Treat (ITT) Population. Patients will be considered to have progression to IMV and/or ECMO or death based on the [Cao et al. \(Table 3\)](#) clinical status assessment of 6 or 7. Specifically, the proportion of patients with progression to IMV and/or ECMO or death by Day 28 (+/- 2 days) will be calculated in each treatment arm as:

- (Number of patients with clinical status of 6 or 7 at any time on or before Day 28 (+/- 2 days)) / (Number of patients in the ITT population)

Patients who discontinued early and did not progress to IMV and/or ECMO or death (a clinical status of 6 or 7) will be considered as having progression unless they were discharged from the clinical facility (discharge date is not missing), in which case they will be considered non-progression.

Patients will be summarized based on the randomized (planned) treatment arm. Patients can meet this endpoint in two ways by progressing to IMV and/or ECMO or dying.

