### Efficacy

#### Primary Endpoint

The primary efficacy endpoint is the proportion of patients who progress to IMV and/or ECMO or death during the 28 days following randomization.

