### **3 STUDY DESIGN**

This is a Phase 2 randomized, double-blind, placebo-controlled, multicenter study to evaluate the efficacy and safety of pacritinib in hospitalized patients with severe COVID-19 with or without cancer. Severe COVID-19 is defined as confirmed disease in patients who are hospitalized with hypoxia ( $\text{SpO}_2 \leq 93\%$  on room air), respiratory rate  $>30$ ,  $\text{PaO}_2/\text{FiO}_2 <300$ , but do not require IMV.

Patients will be randomized 1:1 to receive pacritinib (400 mg QD on Day 1, then 200 mg BID from Day 2 to Day 14) + SOC or placebo + SOC stratified by age (< 60 years versus  $\geq 60$  years) and the 7-point ordinal scale of clinical status scale (baseline 3 or 4 versus 5). The study duration will be 8 weeks.

Assigned treatment will continue for up to Day 14 or until the patient experiences intolerable adverse events (AEs), withdraws consent, or initiates another investigational therapy, or until the study is terminated. Assigned therapy may be given for an additional 7 days (for a total of 21 days) with the approval of the Medical Monitor if, in the opinion of the investigator, the patient's clinical signs and symptoms are improving and the potential benefit outweighs the potential risk. In the event of hospital discharge, patients will complete treatment with the assigned therapy as an outpatient.

The primary endpoint is the effect of treatment on the proportion of patients who require IMV and/or ECMO or die by Day 28.

The study will be monitored by an IDMC comprising a multidisciplinary group of at least three voting members in the fields of hematology, infectious disease, and biostatistics. Additional personnel may be added to the IDMC at the request of the IDMC membership. The membership, roles, and responsibilities of the IDMC will be fully defined by an IDMC charter.

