## **7 STUDY ASSESSMENTS**

### **7.1 Criteria for Evaluation**

#### **7.1.1     *Efficacy***

##### **7.1.1.1     *7-Point Ordinal Scale of Clinical Status***

The following 7-point ordinal scale of clinical status ([Cao et al 2020](#)) will be used to assess the ordinal scale secondary endpoints. The ordinal scale score is to be documented daily on study through Day 28 for all patients, including those who have been discharged from the hospital.

1. Not hospitalized with resumption of normal activities
2. Not hospitalized but unable to resume normal activities
3. Hospitalization, not requiring supplemental oxygen
4. Hospitalization, requiring supplemental oxygen not meeting criteria for categories 5 or 6
5. Hospitalization, on non-invasive positive pressure ventilation or high-flow nasal cannula

6. Hospitalization, requiring IMV and/or ECMO
7. Death

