#### **7.1.4.2        *Randomization (Study Day -1 or 1)***

Patients must have provided informed consent, then completed all Screening procedures, and met all eligibility criteria.

Note: Screening and randomization may occur on either Day -1 or Day 1. Patients may be screened, randomized, and start treatment on the same day (Day 1).

- AE reporting will begin at the time of randomization

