#### **7.1.4.3        *Study Day 1 (Pre-dose)***

Note: Patients may be screened, randomized and start treatment on the same day.

- Randomization
- 7-point ordinal scale of clinical status (unless the same time point as Screening)
- Physical examination (any physical examination performed as part of routine care on Day 1 prior to signing of informed consent may be used for documentation)
- Maximum documented temperature in the 24 hours prior to dose of pacritinib/placebo ( $T_{max}$ )
- Maximum documented heart rate in the 24 hours prior to dose of pacritinib/placebo ( $HR_{max}$ )

- Documentation of oxygen delivery method (unless the same time point as Screening). If multiple delivery methods were used, the method that provides the highest concentration of oxygen will be documented.
- Highest oxygen delivery flow rate (if on non-invasive oxygen)
- Highest %FiO2 (if on CPAP, BiPAP, or IMV)
- Highest PEEP (if on positive pressure ventilation)
- Begin pacritinib/placebo dosing
- Document pacritinib/placebo dosing
- AEs
- Concomitant medications

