#### 7.1.4.8 *Outpatient Assessments*

- 7-point ordinal scale of clinical status (Daily scores through Day 28 will be evaluated and will be based on weekly assessments performed on Day 8, Day 15, Day 22, and Day 28 [ $\pm 2$  days].)
- Documentation of pacritinib/placebo dosing for patients who continue treatment after discharge from the hospital
- AEs (will be documented through 30 days after the last dose of pacritinib/placebo and will be based on weekly assessments [ $\pm 2$  days] through 30 days after last dose)

- Concomitant medications (will be documented through 30 days after the last dose of pacritinib/placebo and will be based on weekly assessments [ $\pm 2$  days] through 30 days after last dose)

Note: Outpatient assessments should be based on weekly telephone/videoconference communication with the patient and include an evaluation of the **daily** 7-point ordinal scale score for the days between contacts and daily pacritinib/placebo dosing as outlined in [Table 1](#). More frequent telephone/videoconference contact may occur as needed to supplement the above assessments. Review of medical records may also be performed as needed to supplement these assessments; medical records should be reviewed for patients who cannot be reached by telephone/videoconference.

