## **11.1 Endpoints for the Analysis**

### **11.1.1 *Efficacy***

#### **Primary Endpoint**

The primary efficacy endpoint is the proportion of patients who progress to IMV and/or ECMO or death during the 28 days following randomization. The proportion is calculated as the number of patients who progress divided by the total number of patients in the ITT population.

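### The SAP adds an undeclared +/- 2 day window to the primary endpoint, so the last day on which an event counts is not fixed

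*SAP*

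**What the plan says.** **Protocol.** Section 11.1.1 and the synopsis agree: "The primary efficacy endpoint is the proportion of patients who progress to IMV and/or ECMO or death during the 28 days following randomization". The objectives and section 3 use a shorter form, for example "The primary endpoint is the effect of treatment on the proportion of patients who require IMV and/or ECMO or die by Day 28". None of these carries a window.

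**Protocol, day count and data collection.**
- Section 7.1.4.2: "Screening and randomization may occur on either Day -1 or Day 1".
- Section 7.1.4.3 puts "Begin pacritinib/placebo dosing" on Study Day 1.
- Section 7.1.1.1: "The ordinal scale score is to be documented daily on study through Day 28 for all patients".
- Section 7.1.4.8: for outpatients, the daily scores through Day 28 "will be based on weekly assessments performed on Day 8, Day 15, Day 22, and Day 28", each contact with a tolerance of 2 days either side.

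**SAP.**
- Section 6.1 gives the primary numerator as "Number of patients with clinical status of 6 or 7 at any time on or before Day 28 (+/- 2 days"; the same window appears in the endpoint sentence above it.
- Section 7.1.1 sets Study Day 1 at first dose and notes that randomization may come earlier.
- Section 7.4.1 describes the binary analysis as events by Day 28, without a window. Its time-to-event formula runs from randomization.
- The footnote to Table 6 admits dates up to study Day 30, although one censoring row in that table refers to no event by Day 28. Table 7 (time to improvement) has the same Day 30 footnote.
- Section 6.2.2 defines 28-day mortality over the 28 days following randomization.
- Section 9 says that no changes from the protocol analysis are planned.

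**The concern.** A cumulative endpoint needs one last day. An at-any-time, on-or-before rule combined with a two-sided tolerance can be read as Day 26, 28 or 30. Table 6 shows the SAP itself using the upper edge, while the binary text of 7.4.1 uses Day 28. The choice could end up being made in programming, after data have accrued.

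Three consequences follow if Day 30 is used:
- The primary endpoint covers a longer period than the protocol's, and SAP 9 does not say so.
- Status on Days 29 and 30 is not scheduled, so late events would be captured unevenly and would be mainly deaths.
- A death on those days could count in the composite and yet be outside the 28-day mortality endpoint.

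There is a separate gap in the day origin. If the first-dose origin of SAP 7.1.1 is applied to Day 28, a patient who is randomized but never dosed is in the ITT denominator with no defined cut-off.

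**Working it through.** **1. The plan's own sample size.** Inputs (protocol 11.6, SAP 3.4): 26.5% versus 13.5%, one-sided alpha 0.10, power 80%, 1:1. The two-proportion formula with continuity correction gives 100 per arm, N = 200, which matches the plan. Without the correction it gives 85 per arm. A cut-off rule enters neither calculation, so N does not change.

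**2. Where the cut-offs fall.** Let R be the randomization date. Assume no Day 0 and dosing no later than the day after randomization.

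| Randomized on | First dose | Study Day 28 | Study Day 30 |
|---|---|---|---|
| Day 1 | R | R+27 | R+29 |
| Day -1 | R+1 | R+28 | R+30 |

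The protocol's 28 days can end at R+28 (28 elapsed days) or at R+27 (randomization counted as day 1, as in the SAP's + 1 formulas). Study Day 30 is then 1 or 2 days past R+28, or 2 or 3 days past R+27.

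**3. Extra events.** The documents give no event timing, so this step is illustrative. Assume the planning rates hold at 28 days with 100 per arm, giving 26.5 + 13.5 = 40 events.

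Cumulative hazard at 28 days: H28 = -ln(1 - p), which is 0.3079 for placebo and 0.1450 for pacritinib. Event probability at day t: 1 - exp(-H28 x (t/28)^k). k = 1 is a constant hazard. k = 0.5 is front-loaded, with about 73% of the 28-day events by day 14.

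Expected events, both arms together:

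| t (days) | k = 1 | k = 0.5 |
|---|---|---|
| 27 | 38.74 | 39.37 |
| 28 | 40.00 | 40.00 |
| 29 | 41.25 | 40.62 |
| 30 | 42.49 | 41.23 |

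- Against R+28: 1.25 or 2.49 extra events (k = 1), 0.62 or 1.23 (k = 0.5). Range 0.6 to 2.5. The 2.49 splits as 1.60 placebo and 0.89 pacritinib.
- Against R+27: 2.51 or 3.75 (k = 1), 1.26 or 1.86 (k = 0.5). Range 1.3 to 3.8.

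**4. Power at 100 per arm.** With p̄ the mean rate, d the difference, n = 100 and z = 1.2816:

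power = Φ{[d - z√(2p̄(1-p̄)/n)] / √[(p1(1-p1) + p0(1-p0))/n]}; the continuity-corrected version replaces d by d - 1/n.

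| t (k = 1) | Uncorrected | Corrected |
|---|---|---|
| 27 | 0.839 | 0.791 |
| 28 | 0.849 | 0.803 |
| 30 | 0.865 | 0.823 |

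From 28 to 30 days the change is 1.6 points uncorrected and 2.0 corrected. From 27 to 30 it is 2.6 and about 3.2. With k = 0.5, uncorrected power goes from 0.849 at day 28 to 0.857 at day 30.

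**The case against.** The best defence is that this is only a visit window. Protocol 7.1.4.8 allows 2 days either side of the Day 28 outpatient contact, SAP 7.4.2.3 uses the same tolerance for tabulating status at Day 28, and the protocol leaves analysis detail to the SAP. That is probably where the window came from, and it stands as an explanation. It does not cure the wording. A contact on Day 30 supplies scores through Day 28; it does not extend the period in which events count. Table 6 uses the window as an event limit.

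It can also be said that the internal SAP conflict is mild. Section 7.4.1 may only be repeating the protocol's shorthand, Table 6 governs an additional analysis, and 6.1 read at its upper edge agrees with Table 6. That has some force. The firmer conflict is between the SAP and the protocol, and it remains.

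Stronger readings are tempting and are not supported:
- **That SAP 6.1 counts from first dose.** It does not say so. The origin is inferred from 7.1.1, a baseline section, while the SAP's time-to-event formulas and mortality definitions run from randomization. The protocol shares the ambiguity, because it uses Day 28 beside 28 days following randomization and its Day 1 is the dosing day.
- **That the sponsor intends a Day 30 primary endpoint.** The binary text of 7.4.1 and SAP 9 point the other way.
- **That the window favours one arm.** Two additional events in one arm only would move uncorrected power to 73.7% (both on pacritinib) or 91.1% (both on placebo). The rule is identical in both arms, and nothing in the documents suggests a one-sided effect.

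**Conclusion.** The point holds as an undeclared and imprecise change to the primary endpoint definition, and it should be fixed before unblinding. What is new in the SAP is the window; the uncertainty about day origin is partly inherited from the protocol.

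The likely effect is small, and the event counts above are upper figures, because they assume full capture on days when status is not scheduled. They depend on the planning rates and on two assumed hazard shapes, neither of which the documents supply. No bias between arms is shown. The reason to act is that the cut-off decides which patients are primary events, and the present text does not settle it.

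**What to change.** 1. Delete the +/- 2 days from SAP 6.1, and replace the Day 30 limit in Tables 6 and 7 with the same cut-off as the binary analysis.
2. State once that the cut-off is 28 days following randomization for every ITT patient, dosed or not, and write the last included calendar date. The literal elapsed-day reading is R+28; the SAP's + 1 formulas imply R+27, so the text must name one. R+28 keeps all scheduled Day 28 scores but reaches study Day 29, where status is not scheduled, for patients randomized on Day 1. R+27 drops the scheduled Day 28 score of patients randomized on Day -1.
3. Apply the same origin and count to the primary endpoint, mortality, time to improvement, ventilator-free days (SAP 6.2.1) and immunomodulatory use (SAP 6.2.5). The last two are written from Day 1 in the SAP and from randomization in protocol 11.1.1.
4. Keep +/- windows only for contact timing and for the visit tabulation in SAP 7.4.2.3.
5. If Day 30 is intended, say so in 6.1, in the binary text of 7.4.1 and in Table 6, and declare and justify it in SAP 9.

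The cost is SAP wording and programming, with no new data and no change to planned N. Relative to a Day 30 reading, the events forgone are those in the ranges worked out above.
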